Prior to initiation of the trial, the DSM will review and approve the study design and plans for recruitment, adherence, interventions, data quality, and safety monitoring. At periodic intervals during the course of the trial, the DSM will evaluate the adequacy and timeliness of participant recruitment, evaluate the ability of the trial to reach stated goals, review adherence to visits and protocols, assess data quality and timeliness, evaluate the safety of participants, provide a report to the investigators and the IRB on the scientific progress of the trial and the safety of participants, make recommendations to the investigators on continuation, termination, or other modifications of the trial, and consider factors external to the study (i.e., new scientific or therapeutic developments) when relevant to the safety of the participants or the ethical conduct of the trial.

The DSM will periodically review aggregate and unblinded trial data after 30, 60, 90, and 120 participants complete the 6-week visit. An emergency meeting may also be called by the principal investigator at any time should questions of participant safety arise. Each review will include an assessment of the adequacy and timeliness of participant recruitment, adherence to the visit and intervention protocols, data quality and timeliness, adverse effects, and participant safety.

Given that the study is of short duration, no assessment of interim efficacy will be done, and the study will not be stopped or altered for unexpected efficacy or lack of efficacy. Interim reports for the DSM will be prepared by an unblinded biostatistician at the Women's Health Clinical Research Center, and sent to the DSM at least 5 days prior to a pre-scheduled meeting or conference call. A copy of the interim reports will be retained in a locked, confidential file by the DSM.

After each interim review, the DSM will provide a signed statement that indicates whether the study should continue, terminate, or be altered based on ability to meet study recruitment and data quality goals and participant safety. He will include any recommendations for changes to the protocol if necessary to enhance participant safety or potentiate the ability of the trial to answer the research hypotheses. This statement will be provided to the principal investigator and will be sent to the UCSF IRB and to the NIA program officer. All materials, discussions, and proceedings of the DSM process will be completely confidential.

D.9 Data Management Plan

D.9.1 Overview

Data will be entered, managed, edited and secured by the UCSF Data Management Group (DMG) which enables simple real-time electronic data entry, ensures timely identification and resolution of data discrepancies, and facilitates the transformation of data to SAS for viewing, reporting, and analyses. Most of the forms and database management modules required for the proposed trial have already been developed and used in previous studies.

D.9.2 Data collection & editing

Machine-readable data forms created with Teleform® software and available for printing at the clinical site from the study website will be completed by participants and clinic staff and transmitted to the DMG using a standard fax machine. The data forms are received at the DMG as electronic images and are evaluated automatically for duplication errors or incomplete scanned images and verified manually by a staff member using Verifier software. This is an important step in which possible misinterpretations in the automated input of data are corrected (e.g. misreading a particular text entry). As each form is verified, the data are written to a pre-defined Microsoft SQL Server database. All of the original form images can be viewed via the password-protected study website. Every hour, preprogrammed error-checking programs scan incoming forms for completeness, data ranges and logic sequences. The results of the error-checking procedures are posted to the study web site where clinical site personnel monitor successful transmission of forms and address any errors that have been detected. Thus, data cleaning is an ongoing process throughout the trial facilitating rapid analysis of results after the final participant visit.

D.9.3 Data monitoring reports

Data are monitored on an ongoing basis to produce a number of standard reports that are made available on the study website automatically, including recruitment reports comparing goal versus actual recruitment rates; adherence reports comparing the number of expected visits to actual visits; participant retention reports indicating the number of participants active, completed, lost, etc.

D.9.4 Computer & data security

The UCSF DMG follows standard operating procedures for computer system security in compliance with established standards for Information Technology Security. The network is privately maintained, hardware fire-walled and none of the workstations or database servers can be directly addressed from outside the Local Area Network. All study data will be stored on Microsoft SQL servers that are backed-up nightly to disk and mirrored to a “failover” site at a co-location facility in San Francisco. In addition, back-up copies of the entire enterprise are archived in Sacramento, CA by Recall, Inc. to protect study data in case of a natural disaster in the San Francisco Bay Area. All servers are housed in a state-of-the-art secure server room with controlled access. All servers are protected from viruses by Network Associates Netshield 4.x, Groupshield, and VirusScan Enterprise 7.x (McAfee, Santa Clara, CA). This software automatically checks for virus signature file updates from Network Associates’ FTP and HTTP sites once an hour.

D.10 Statistical Considerations

D.10.1 Statistical analysis plans

Aim 1: To determine whether a device-guided slow-breathing exercise program can reduce the frequency

and severity of OAB symptoms in women.

Expected outcomes: Compared to controls, women randomized to slow breathing will demonstrate a more than 20% greater reduction in frequency of voiding or incontinence episodes associated with moderate urgency, as well as greater reductions in other OAB symptoms and in impact of symptoms.

The primary outcome will be change in the frequency of any voiding or incontinence episodes associated with at least moderate urgency (measured over 3 days using the validated voiding diary and urgency scale²⁹⁻³¹) from baseline to 12 weeks. Treatment effects will be estimated using ANCOVA models, adjusting for baseline frequency of the outcome. Analyses will be by intention to treat, according to treatment assignment, and without regard to adherence with use of the active or control interventions. For additional confirmation of treatment effects on this primary outcome, we will also use ANCOVA models to examine treatment effects on frequency of other OAB symptoms, including 1) urgency incontinence, 2) voiding or incontinence episodes associated with a *severe* sensation of urgency, 3) total daytime and nighttime voiding (regardless of whether they are associated with urgency), and 4) Overactive Bladder Symptom Composite Scores, as well as on scores on validated urinary symptom bother and impact questionnaires (i.e., the OAB-Q, USIQ, UDI-6, PPBC, and PSQI). Outcomes will be transformed if Shapiro-Wilk tests for normality of the residuals from initial models are significant at $p < 0.01$. In secondary analyses, if treatment benefits are detected at 12 weeks, we will also assess for persistence of effects 12 weeks post-treatment using data from the 24-week mail-in diary and questionnaires, and assess for dose response in treatment effects based on duration and cumulative time of treatment exposure (see the “Additional statistical issues” section below).

Aim 2: To determine whether this slow-breathing intervention can improve autonomic nervous system control in women with OAB, and explore change in autonomic control as a mechanism of treatment effects on OAB symptoms.

Expected outcomes: Women randomized to practice slow-breathing will demonstrate significantly improved autonomic control as measured by high-frequency heart rate variability and pre-ejection period parameters, and that treatment effects on OAB symptoms will be at least partly mediated by improvements in autonomic control.

Secondary outcomes include 12-week change in autonomic control as assessed by high frequency heart rate variability (RSA) and pre-ejection period (PEP), as the purest available measures of parasympathetic and sympathetic function. Treatment effects on each of these measures will initially be estimated using ANCOVA models, first to examine effects on resting parameters, followed by examination of effects on rest-to-stress change (i.e., reactivity) while adjusting for baseline levels of each parameter. Treatment effects will again be examined by intention to treat, according to treatment assignment, and without regard to adherence. Autonomic parameters will be transformed as necessary if their distributions appear significantly skewed. We will then assess for mediation of treatment effects on OAB symptoms by improvement in autonomic control using structural equation modeling. This will involve fitting an initial model that includes both autonomic parameters and anxiety symptoms (as described below in the statistical plan for Aim 2), then extracting coefficients for each of the hypothesized mediating pathways.

Aim 3: To determine whether this slow-breathing intervention can improve anxiety-related symptoms in women with OAB, and explore changes in anxiety as a mediator of treatment effects on OAB symptoms.

Expected outcomes: Women with OAB randomized to practice slow-breathing exercises will report significant improvement in anxiety-related symptoms (as measured by validated questionnaires), and treatment effects on OAB symptoms will be at least partly mediated by improvement in anxiety.

Additional outcomes will include change in anxiety symptoms from baseline to 12 weeks, measured by scores on the validated STAI, HADS, PSS, and BDI questionnaires. Intervention effects will again be estimated using ANCOVA, adjusted for baseline questionnaire scores. Anxiety symptom outcomes will be transformed as necessary if their distributions appear skewed. To assess for mediation of treatment effects on the primary outcome by change in anxiety symptom scores (as well as autonomic parameters as noted in the statistical plan for Aim 2), we will use structural equation modeling as outlined above).

D.10.2 Sample size estimates

Sample size is calculated based on parameter estimates derived from prior trials conducted by the investigators, such as BRIDGES and PRIDE:^{64,65} a) mean baseline frequency of urgency- associated voiding or incontinence episodes of 12; b) mean reduction in frequency in controls of 30%; c) standard deviation (SD) of change in urgency-associated voiding or incontinence frequency of 5.8 and d) correlation between baseline and follow-up values of 0.59. We assume that a clinically significant effect in the primary outcome would be a net reduction in the active group of more than 20% than that of controls. Under these assumptions, a sample size of 160 (80 per group) would provide 80% power in 2-sided tests with type-I error of 5% to detect between-group differences of >20% in the active vs. control arm. This accounts for reduction in the residual variance achieved by adjustment for baseline frequency, as well as loss to follow-up of 15%. In comparisons of changes in secondary outcomes (other OAB symptoms, impact scores, anxiety, and autonomic parameters), the sample will provide 80% power in 2-sided tests with type-I error of 5% to detect differences of 0.5 SDs, depending on within-subject correlation of outcomes, assumed to fall in the range of 0.4 to 0.8.

D.10.3 Drop-out rates

Given that the proposed trial is of short duration, dropout levels are expected to be low (i.e., less than 15%). The assumption of non-informative dropout will be examined by comparing baseline and early post-randomization characteristics of dropouts and non-dropouts. If dropout is differential between groups, analyses will be adjusted for maldistributed variables. In a sensitivity analysis, we will also use multiple imputation of missing outcomes, in conjunction with standard methods for calculating summary estimates, confidence intervals, and p-values.⁶⁶

D.10.4 Dose effects

In the event that treatment appears effective in improving OAB symptoms over 12 weeks, we will use a closed test procedure to assess for a dose response in duration of treatment without inflating type-I error:⁶⁷ specifically, if we detect a statistically significant benefit over 12 weeks at an alpha of 0.05, we will then assess change from baseline to 6 weeks, and from 6 to 12 weeks, also at alpha of 0.05. In exploratory

analyses, we will also assess for a dose response in cumulative time of effective breathing practice, by examining the relationships between total minutes of effective practice and OAB outcomes at 12 weeks, controlling for baseline levels of outcomes. These analyses will allow for assessment of the extent to which differences in adherence and treatment exposure influence treatment benefits on OAB.

D.10.5 Subgroup analyses

Differences between treatment groups will be analyzed in pre-defined subgroups based on clinicopathologic factors in multivariate analysis. For example, we will explore whether high baseline levels of autonomic imbalance or anxiety, past use of medications or other OAB treatments, or baseline use of psychoactive medications influence treatment-associated changes in outcomes. Subgroup-specific effect estimates will be considered only if the interaction with the subgroup is significant at $p < 0.05$.

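### A Shapiro-Wilk pre-test sets the scale of the primary analysis, so the main result may not come out in the episodes on which the trial was sized

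*Combined protocol and SAP*

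**What the plan says.** Combined protocol and SAP, D.10.1 (Aim 1), defines the endpoint: "The primary outcome will be change in the frequency of any voiding or incontinence episodes associated with at least moderate urgency", from baseline to 12 weeks on a 3-day diary. The model is stated next: "Treatment effects will be estimated using ANCOVA models, adjusting for baseline frequency of the outcome". After listing the secondary bladder outcomes, the same paragraph adds: "Outcomes will be transformed if Shapiro-Wilk tests for normality of the residuals from initial models are significant", with a threshold of p < 0.01. The sentence follows both the primary and the secondary outcomes and exempts neither.

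Nothing in the document names the transformation, says whether it applies to the change score or the 12-week count, says whether baseline is transformed too, or asks for a back-transformed or parallel result in episodes.

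D.10.2 sizes the trial in untransformed episodes, starting from a "mean baseline frequency of urgency- associated voiding or incontinence episodes of 12" and an SD of change of 5.8. The target, in the Specific Aims and again in D.10.1, is worded as a reduction more than 20% greater than in controls.

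Under Aim 3 there is a looser rule, "Anxiety symptom outcomes will be transformed as necessary if their distributions appear skewed", and Aim 2 has a similar one. These concern anxiety and autonomic outcomes only and are not part of this point.

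**The concern.** A p-value computed on the trial data decides the scale on which the primary effect is estimated. If the test is significant, the plan moves from a difference in episodes, which is what the sample size assumes, to an unspecified scale. The team would have to choose that scale after fitting the first model. A reader could not tell in advance whether the headline result will be in episodes, as a ratio, or as something else. In some trials the two scales would also fall on opposite sides of p = 0.05.

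**Working it through.** **1. The plan's own figure.** Inputs from D.10.2: baseline mean 12 (taken as per 3 days, since the period is not stated there), control reduction 30% (12 to 8.4), SD of change 5.8, correlation 0.59, 15% loss, 80 per arm. I read the 20% as 20% of baseline, 0.20 × 12 = 2.4 episodes, and take equal SDs at both visits.

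- SD of the count = 5.8/√(2(1 − 0.59)) = 6.405.
- ANCOVA residual SD = 6.405 × √(1 − 0.59²) = 5.171.
- Analysed per arm = 80 × 0.85 = 68.
- Power at 2.4 episodes = 77.2%. The difference detectable with 80% power is (1.960 + 0.842) × 5.171 × √(2/68) = 2.48 episodes, or 2.48/12 = 20.7% of baseline.

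At exactly 2.4 episodes the formula gives 73 per arm, and 73/0.85 = 86, so 172 in total. Since the plan speaks of differences above 20%, 20.7% fits its wording and I do not call 160 wrong. What matters here is that the sizing is on the episode scale.

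**2. Are normal residuals plausible?** Inclusion criterion 4 in D.2 requires at least 9 qualifying episodes in 3 days, and the follow-up count cannot fall below zero. For a control woman entering at 9, the predicted 12-week count is 8.4 + 0.59 × (9 − 12) = 6.63. Zero lies 6.63/5.171 = 1.28 residual SDs below that, so a normal residual would put about 10% of such women below zero. With a 2.4-episode effect the figures are 4.23/5.171 = 0.82 SDs and about 21%. Some skewness is therefore expected on the plan's own inputs.

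**3. How often the rule fires, and what follows.** Simulation with 68 per arm and 4,000 trials per row: ANCOVA on change, Shapiro-Wilk on the residuals at 0.01, and ANCOVA on log(count + 1) if triggered. Baseline is 9 plus a negative binomial excess with mean 3. Follow-up is Poisson around 70% of baseline, with gamma variation (shape 2, 4 or 8) and a 2.4-episode mean effect where there is one. The distributions and the log are assumptions, because the plan gives neither. Trigger, power and disagreement are under the effect.

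| Data | SD of change | Correlation | Trigger | Type I, episodes | Type I, two-stage | Power, episodes | Power, two-stage | Scales disagree |
|---|---|---|---|---|---|---|---|---|
| Normal | 5.7 | 0.59 | 1.2% | 5.1% | 5.1% | 76.6% | 76.6% | not run |
| Counts, shape 2 | 6.9 | 0.37 | 99.4% | 4.6% | 5.1% | 64.0% | 59.0% | 16.6% |
| Counts, shape 4 | 5.4 | 0.47 | 90.9% | 4.9% | 4.8% | 83.5% | 81.2% | 10.1% |
| Counts, shape 8 | 4.4 | 0.55 | 71.5% | 4.5% | 5.0% | 95.8% | 94.9% | 3.8% |

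Under the null, the three count rows triggered in 99.5%, 91.2% and 69.1% of trials.

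**4. Other assumed distributions.** Log-normal-Poisson counts with baseline at least 9 triggered in 44–64% of trials over four settings. The setting closest to the plan (SD of change 5.80, correlation 0.64, control reduction 30.6%) gave 64%, but its baseline mean was 16.2, not 12. A second set gave 69% at an SD of change of 5.76 and about 90% in two noisier settings, with correlations of 0.28–0.42. A further set of count simulations gave 82–97%, with the scales disagreeing in 6–12% of trials under an effect. Across all the simulations, untransformed ANCOVA had type I error of 3.8–5.8%.

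**The case against.** The strongest reply is that the trigger and its threshold are fixed in advance, so this is a written rule and not free choice, and it does no inferential damage. Most of that stands. Two-stage type I error is near nominal, and the power cost is small.

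Four stronger readings are tempting, and the documents do not support them.

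- **Inflated type I error.** A reader might infer this from the words data-driven and pre-test. The simulations show none from the pre-test with any one transformation. If someone tried log, square root and rank and kept the most favourable, type I error was 6.4–7.3% in simulation, but the plan does not provide for that conduct.
- **A choice made with the arms in view.** The test uses pooled residuals after the treatment effect has been removed, so it does not show which arm did better. In simulation the pre-test decision and the treatment estimate correlated at only −0.03 to +0.04.
- **A rule that cannot be carried out.** Log and square root fail on negative changes. But ANCOVA on change and on the follow-up count give the same treatment coefficient when baseline is a covariate, so log(count + 1) of the follow-up count is a defined and natural choice. The gap is that no transformation is named.
- **A transformed result would answer a different question from Aim 1.** Aim 1 is worded as a percentage, so a ratio would not be foreign to it. The plan simply does not specify one, and its sizing inputs are in episodes.

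The trigger rates also depend on assumed distributions. None of the count settings matches the planned mean, SD and correlation all at once, so the rates are a range and not an estimate.

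**Conclusion.** The point holds as a cheap improvement, not as a threat to the trial's validity. If the diary counts are skewed, as the entry floor and the zero bound make likely, the rule would probably fire (44–99% of simulated trials) and move the primary result to an unnamed scale. If the residuals were normal it would almost never fire (about 1%). With a true effect, the choice of scale would change the significance of the result in about 4–17% of trials. Nothing is gained in return: untransformed ANCOVA holds type I error near 5% with 68 per arm, and in the tabulated count settings the two-stage procedure had 1 to 5 points less power. The disagreement figures rest on the assumed count distributions and on log(count + 1) as the transformation.

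**What to change.** In D.10.1, remove the normality pre-test for the primary outcome. State that the single primary analysis is baseline-adjusted ANCOVA on untransformed change in episodes per 3 days, reported in episodes whatever the residuals look like. Robust or bootstrap intervals are optional.

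Name one sensitivity analysis in advance, for example a negative binomial model of the 12-week count adjusted for baseline. This also gives a percentage effect that speaks to the wording of Aim 1.

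For urgency incontinence, any count model needs a baseline term defined at zero, such as log(baseline + 1). Entry can be met on voiding episodes alone, so some women may have no incontinence at baseline.

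The cost is SAP wording, settled before unblinded analysis. The sample size of 160, the visits and the data collection do not change. The downside is possibly slightly less efficiency than an ideal transformation would give.

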All participants, regardless of treatment assignment, will also receive a pamphlet that provides basic patient-directed information about behavioral self-management of OAB, including pelvic muscle exercises and urge suppression. As information about self-management of OAB is available from multiple websites and public resources, systematic provision of this information will minimize differential use of self-management techniques between treatment groups, and also reflect expected concomitant use of these techniques with slow-paced respiration in clinical practice.

D.5 Measurements

D.5.1 Overactive bladder symptoms (assessed at baseline, 6 weeks, and 12 weeks, and 24 week mail-in)

A. Frequency of voiding or incontinence episodes associated with at least moderate urgency

The primary outcome of this trial, change in frequency of any voiding or incontinence episodes associated with at least a moderate sensation of urgency, will be assessed using a validated 3-day voiding diary.^{29,30} At each relevant time point, participants will receive a blank voiding diary along with written instructions and a sample completed diary page. Women will use the diary to record each time they experience a sense of urgency, void in the toilet, or leak urine over 3 days. They will also rate the severity of urgency associated with each of the above episodes using a validated severity scale (the Indevus scale): a) none, b) mild—urgency that is easily tolerated, c) moderate—urgency that interferes with activities, c) severe—extreme urgency that abruptly stops activities).³¹ Urgency that results in urine leakage (incontinence) will be assumed to be severe.

B. Frequency of other OAB symptoms

Data abstracted from voiding diaries will also be used to assess secondary voiding outcomes, including

change in frequency of the following additional OAB symptoms: 1) urgency-type incontinence; 2) any voiding or incontinence associated with severe urgency, 3) total daytime or nighttime voiding (regardless of association with urgency).

Diary data will also be used to calculate an Overactive Bladder Symptom Composite Score (OAB-SCS), in which points are assigned for each episode of urgency incontinence (5 points each), urgency-associated voiding (2 to 4 points depending on the severity of urgency), and non-urgency-associating voiding (1 point).³²

C. Bothersomeness and quality-of-life impact of OAB symptoms

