Twelve weeks after returning their guided-breathing devices, women will complete a final voiding diary and set of questionnaires and mail it back to study staff, using a pre-addressed, pre-stamped envelope.

D.6.10 Time commitment

Telephone screening will require approximately 15 minutes. The screening clinic visit will require up to one and a half hours. The baseline clinic visit will require approximately two hours. The 6-week follow-up visit will require one and a half hours. The final (12-week) visit will require approximately two hours. The one-week and 8-week follow-up telephone calls will each require between 5 and 15 minutes. The total estimated time required for study visits is therefore 7 and a half hours, including 7 and hours of clinic visit time, and approximately one half hour of telephone time.

Additionally, participants must practice either slow-paced respiration or music-listening using their RESPeRATE devices for at least 15 minutes per day for 12 weeks, for a total of 21 hours of home RESPeRATE practice time. They must complete voiding diaries at four timepoints in the study (baseline, 6 weeks, 12 weeks, and 24 weeks), adding another 15 minutes at each of these timepoints. They must also complete a mail-in questionnaire packet at 24 weeks, adding another 30 minutes at this timepoint. The total estimated time required of participants at home is therefore 22 and a half hours. In summary, this 12-week study will require a total of 30 hours of participants' time, including 7 and a half hours of visit time, and 22 and a half hours of home time.

D.7 Adherence, Discontinuation, and Reimbursement

D.7.1 Overview

Every effort will be made to assure that participants adhere to the protocol and use the study interventions regularly. Participant contact information including address, phone number(s), fax number(s), and email

address will be obtained. We will also request contact information for two family members or friends who will be able to locate the participant. The study team will encourage retention by educating participants about the importance of the study, maintaining a friendly and efficient clinical center environment, and encouraging excellent staff-participant rapport. All identifying information will be kept confidential, appropriately secured and destroyed at the end of the trial.

D.7.2 Adherence to interventions

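### The 24-week between-group difference is planned only if an undefined 12-week benefit is detected; it should be estimated and reported whatever the 12-week result

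*Combined protocol and SAP*

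**What the plan says.** Under Aim 1, D.10.1 sets the primary analysis as change from baseline to 12 weeks: "Treatment effects will be estimated using ANCOVA models, adjusting for baseline frequency of the outcome". It then lists other diary outcomes and five questionnaires. Among the secondary analyses, it says that "if treatment benefits are detected at 12 weeks, we will also assess for persistence of effects 12 weeks post-treatment". The stated source for this analysis is the mail-in packet ("using data from the 24-week mail-in diary and questionnaires"). No outcome and no significance level is attached to that condition. No other part of D.10 plans a 24-week between-group comparison.

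Data collection carries no such condition. D.5.1 lists the bladder outcomes as "assessed at baseline, 6 weeks, and 12 weeks, and 24 week mail-in", D.5.3 schedules the anxiety and stress scales at 24 weeks as well, and Appendix A marks the mail-in column for both. D.6.9 says that twelve weeks after returning their devices "women will complete a final voiding diary and set of questionnaires and mail it back to study staff".

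D.10.4 has a defined gate, "if we detect a statistically significant benefit over 12 weeks at an alpha of 0.05", but it applies to the dose-duration tests. Those cover baseline to 6 weeks and 6 to 12 weeks, not 24 weeks.

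**The concern.** The trial follows women for 12 weeks after the devices go back, but commits to estimating the 24-week difference only when an earlier result is favourable. The 12- and 24-week estimates share participants and baseline values, so their chance errors are expected to run in the same direction. Keeping the second only when the first is favourable carries part of the first one's good luck into the second. When week 12 misses, the plan provides no 24-week estimate at all, so a later difference in either direction has no planned place in the report.

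The undefined trigger adds to this. The sentence follows a list of about ten outcomes and speaks of benefits in the plural. Whether the 24-week analysis is due could be decided after the 12-week results are known.

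**Working it through.** **Inputs from D.10.2.** Baseline mean 12 episodes, SD of change 5.8, baseline-to-follow-up correlation 0.59, 80 per arm, 15% loss (80 × 0.85 = 68 per arm), two-sided 5%.

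**Assumptions not in the documents.**
- SDs are equal at each time, and the standard error is the same at 12 and 24 weeks, with 68 per arm at both.
- The gate is a favourable z > 1.96 on the primary outcome.
- The 12-to-24-week correlation r lies between 0.4 and 0.8. This borrows the within-subject range that D.10.2 gives for secondary outcomes.

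**Step 1: reproduce the plan's figure.** D.10.2 says that "a sample size of 160 (80 per group) would provide 80% power in 2-sided tests with type-I error of 5" per cent "to detect between-group differences of >20% in the active vs. control arm".
- SD at one time = 5.8/√(2 × (1 − 0.59)) = 6.405.
- ANCOVA residual SD = 6.405 × √(1 − 0.59²) = 5.171.
- SE = 5.171 × √(2/68) = 0.887.
- Difference detectable with 80% power = (1.960 + 0.842) × 0.887 = 2.485 episodes, or 20.7% of 12.

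This fits a difference of more than 20% of baseline. At exactly 20% (2.4 episodes) power is 77.2%. The figure matters here only because it supplies the SE.

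**Step 2: correlation of the two adjusted estimates.** With baseline adjusted for at both times, ρ = (r − 0.59²)/(1 − 0.59²).
- r = 0.4: (0.4 − 0.3481)/0.6519 = 0.08.
- r = 0.8: (0.8 − 0.3481)/0.6519 = 0.69.

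**Step 3: chance that the gate opens.** The observed 12-week difference must exceed 1.96 × 0.887 = 1.74 episodes. For a true 12-week effect δ, a = 1.96 − δ/0.887 and P(open) = 1 − Φ(a).
- δ = 2.4: a = −0.746, P(open) = 77.2%. No 24-week estimate is planned in 22.8%.
- δ = 1.2: a = 0.607, P(open) = 27.2%. No 24-week estimate is planned in 72.8%.

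**Step 4: bias in the 24-week estimate when it is reported.** Treating the two estimates as bivariate normal, bias = ρ × SE × φ(a)/(1 − Φ(a)). The part after ρ is 0.347 episodes for δ = 2.4 and 1.082 for δ = 1.2.

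| True effect at both times | ρ = 0.08 | ρ = 0.69 |
|---|---|---|
| 2.4 | +0.028 (1.2%) | +0.240 (10.0%) |
| 1.2 | +0.086 (7.2%) | +0.750 (62.5%) |

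The table uses unrounded ρ (0.0796 and 0.6932).

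**Step 5: type I error at 24 weeks.** Suppose there is no true 24-week effect. A false favourable 24-week result now requires passing the gate and also z > 1.96 at 24 weeks. The probability of both cannot exceed that of the second alone, 2.5%. For example, with a true 12-week effect of 1.2, the bivariate normal rate among trials that pass the gate is 3.1% to 8.4%. Multiplied by the 27.2% that pass, the overall rate is 0.8% to 2.3%.

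**Step 6: with unconditional reporting.** The gate contributes no bias over all trials, and an estimate exists in every trial with a 95% half-width of about 1.96 × 0.887 = 1.74 episodes.

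**The case against.** Gating a secondary test on the primary result is a recognised sequential procedure, and persistence presupposes a benefit that could persist. The analysis is labelled secondary, and 24-week persistence appears in none of the three aims. This stands as far as a confirmatory test or claim is concerned. It does not justify making the estimate conditional too.

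The size is uncertain. Neither the 12-to-24-week correlation nor the gate is specified. If a benefit on any of the listed outcomes opened the gate, it would open more often than calculated. At the design effect the bias is at most about 0.24 episodes, roughly a quarter of a standard error; the large percentages need a true effect of half that. All of this stands, and it is why the result is given as a range.

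Four stronger readings are tempting, and the documents do not support them.
- A reader might infer that the 24-week data are discarded after a 12-week miss. The plan is silent on what happens then; it says only when persistence will be assessed.
- A reader might infer that data exist for all women. The assessment is a mail-in, so they exist for those who return it.
- A reader might take the raised false-favourable rate among reported analyses as inflated type I error. That rate is conditional on passing the gate; the overall rate stays at or below 2.5%.
- A reader might expect the change to correct the number in a trial that passes the gate. The same ANCOVA gives the same estimate there.

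**Conclusion.** The point holds as one about selective estimation and an undefined trigger. D.10.1 commits to the 24-week difference only after a favourable 12-week finding, does not say what counts as one, and leaves a scheduled outcome without a planned estimate otherwise. The upward direction of the bias needs only a positive correlation between the two estimates. Its size rests on the assumed gate, SE and correlation range: modest at the design effect, and potentially large at half of it. At the design effect the more telling figure is that about one trial in four or five (22.8%) would have no planned 24-week estimate.

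The primary analysis is unaffected, and gating a confirmatory persistence claim remains legitimate. The gain from the change is that an estimate exists and is reported in every trial, and that discretion over the trigger is removed. It is worth making before the 12-week results are seen.

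**What to change.** Replace the conditional sentence in D.10.1 with a statement along these lines: the 24-week between-group difference in the primary outcome and in the questionnaires will be estimated by the same baseline-adjusted ANCOVA, by assigned group, in all randomised women with 24-week data. It will be reported with its 95% confidence interval whatever the 12-week result, and the multiple-imputation sensitivity analysis of D.10.3 will be applied to it.

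Keep a 12-week gate only for a confirmatory claim of persistence, and define it as the primary outcome significant at two-sided 0.05. The cost is a short change to D.10.1, one more run of existing models on data already scheduled for collection, and one more secondary estimate to report.
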